#### 5.1.3.2 Adverse Drug Reactions Requiring Avelumab Treatment Discontinuation or Modifications

The following adverse drug reactions (ADRs; for definition, see Section 7.4.1.1) require permanent treatment discontinuation of avelumab:

- Any Grade 4 ADR, except for the following:
  - Grade 4 lipase or amylase abnormality that is not associated with clinical manifestations of pancreatitis. The Medical Monitor must be consulted for such lipase and amylase abnormalities.
  - Grade 4 neutropenia of  $\leq 7$  days in duration
  - Grade 4 thrombocytopenia without bleeding
  - Other single laboratory values out of normal range that do not have any clinical correlate and resolve to baseline within 7 days with adequate medical management.
- Any Grade 3 ADR except for any of the following:
  - Transient ( $\leq 72$  hours) Grade 3 flu-like symptoms or fever, which are controlled with medical management
  - Transient ( $\leq 72$  hours) Grade 3 fatigue, local reactions, headache, nausea, or emesis that resolve to Grade  $\leq 1$  or baseline with appropriate medical management
  - Grade 3 diarrhea or Grade 3 skin toxicity that resolves to Grade  $\leq 1$  in less than 7 days after medical management (eg, immunosuppressant treatment) has been initiated
  - Grade 3 lipase or amylase abnormality that is not associated with clinical manifestations of pancreatitis. The Medical Monitor must be consulted for such lipase and amylase abnormalities.

- Other single laboratory values out of normal range that do not have any clinical correlate
- Tumor flare phenomenon defined as local pain, irritation, or rash localized at sites of known or suspected tumor
- Any Grade 2 ADR should be managed as follows:
  - Infusion should not be given in case of ongoing Grade 2 ADR on the day of trial treatment administration.
  - Treatment can be resumed according to original schedule once ADR resolves to Grade  $\leq 1$ . Up to 2 subsequent study drug doses may be omitted. If more than 2 doses are skipped, treatment may be resumed after consultation with the study Medical Monitor.

See the guidelines for handling infusion-related reactions (Section 6.5.5.1), severe hypersensitivity reactions and flu-like symptoms (Section 6.5.5.2), and irAEs (Section 6.5.5.3).

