### 5.5.1 Withdrawal from Trial Therapy

A subject must be withdrawn from avelumab if any of the following occurs:

- Subject or his/her parent(s)/legal representative(s) withdraw consent.
- Subject lost to follow up.
- Participation in another clinical trial.
- Any events that unacceptably endanger the safety of the subject.
- Subjects meeting the definition of confirmed PD while on treatment based on irRECIST. Subjects who experience confirmed disease progression may be permitted to continue treatment with avelumab per Section 6.2.1.
- Significant clinical deterioration (clinical progression), defined as new symptoms that are deemed by the Investigator to be clinically significant or significant worsening of existing symptoms.
- Unacceptable toxicity.
- Occurrence of an exclusion criterion that is clinically relevant and affects the subject's safety, if trial treatment discontinuation is considered necessary by the Investigator and/or Sponsor.
- Therapeutic failure requiring urgent additional drug (if applicable).
- Occurrence of any Grade  $\geq 3$  ADRs or as defined in Section 5.1.3.2.
- Occurrence of AEs resulting in the discontinuation of the trial treatment being desired or considered necessary by the Investigator and/or the subject.
- Occurrence of pregnancy.
- Use of a prohibited concomitant drug, as defined in Section 6.5.2, where the predefined consequence is withdrawal from the trial treatment if considered necessary by the investigator or the Sponsor.
- Noncompliance (see Section 6.9).

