**Table 5 Management of Immune-related Adverse Events**

Gastrointestinal irAEs		
Severity of Diarrhea/Colitis (NCI-CTCAE v4.03)	Management	Follow-up
Grade 1 Diarrhea: < 4 stools/day over Baseline Colitis: asymptomatic	Continue avelumab therapy Symptomatic treatment, eg, loperamide)	Close monitoring for worsening symptoms Educate subject to report worsening immediately If worsens: Treat as Grade 2, 3, or 4
Grade 2 Diarrhea: 4 to 6 stools per day over Baseline; iv fluids indicated < 24 hours; not interfering with ADL Colitis: abdominal pain; blood in stool	Delay avelumab therapy Symptomatic treatment	If improves to Grade 1: Resume avelumab therapy  If persists > 5 to 7 days or recurs: Treat as Grade 3 to 4
Grade 3 to 4 Diarrhea (Grade 3): ≥ 7 stools per day over Baseline; incontinence; iv fluids ≥ 24 hours; interfering with ADL Colitis (Grade 3): severe abdominal pain, medical intervention indicated, peritoneal signs Grade 4: life-threatening, perforation	Withhold avelumab for Grade 3 Permanently discontinue avelumab for Grade 4 or recurrent Grade 3. 1.0 to 2.0 mg/kg/day prednisone or equivalent Add prophylactic antibiotics for opportunistic infections Consider lower endoscopy	If improves: Continue steroids until Grade 1, then taper over at least 1 month, resume avelumab therapy following steroids taper (for initial Grade 3).  If worsens, persists > 3 to 5 days, or recurs after improvement: Add infliximab 5 mg/kg (if no contraindication), Note: Infliximab should not be used in cases of perforation or sepsis
Dermatological irAEs		
Grade of Rash (NCI-CTCAE v4.03)	Management	Follow-up
Grade 1 to 2 Covering ≤ 30% body surface area	Continue avelumab therapy Symptomatic therapy (eg, antihistamines, topical steroids)	If persists > 1 to 2 weeks or recurs: Withhold avelumab therapy Consider skin biopsy Delay avelumab therapy Consider 0.5 to 1.0 mg/kg/day prednisone or equivalent. Once improving, taper steroids over at least 1 month, consider prophylactic antibiotics for opportunistic infections, and resume avelumab therapy following steroids taper If worsens: Treat as Grade 3 to 4

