Grade 2 AST or ALT > 3.0 to ≤ 5 x ULN and/or total bilirubin > 1.5 to ≤ 3 x ULN	Withhold avelumab therapy Increase frequency of monitoring to every 1 to 2 days	If returns to Baseline: Taper steroids over at least 1 month, consider prophylactic antibiotics for opportunistic infections, and resume avelumab therapy following steroids taper.

	
1.0 to 2.0 mg/kg/day prednisone or equivalent. Add prophylactic antibiotics for opportunistic infections Consult gastroenterologist/hepatologist Consider obtaining MRI/CT scan of liver and liver biopsy if clinically warranted
	If worsens: Treat as Grade 3-4.

Grade 3 to 4 AST or ALT > 5 x ULN and/or total bilirubin > 3 x ULN
	
Discontinue avelumab therapy Increase frequency of monitoring to every 1 to 2 days 1.0 to 2.0 mg/kg/day methylprednisolone iv or iv equivalent Add prophylactic antibiotics for opportunistic infections Consult gastroenterologist Consider obtaining MRI/CT scan of liver and liver biopsy if clinically warranted (for trial sites in Germany, only MRI is to be used)
	
If returns to Grade 2: Taper steroids over at least 1 month If does not improve in > 3 to 5 days, worsens or rebounds: Add mycophenolate mofetil 600 mg/m^2 (for subjects 2 to 18 years of age) twice daily If no response within an additional 3 to 5 days, consider other immunosuppressants per local guidelines

Renal irAEs		
Grade of Creatinine Increased (NCI-CTCAE v4.03)	Initial Management	Follow-up Management

Grade 1 Creatinine increased > ULN – 1.5 x ULN
	Continue avelumab therapy	Continue renal function monitoring If worsens: Treat as Grade 2 to 3 or 4

Grade 2 to 3 Creatinine increased > 1.5 – 6 x ULN
	
Withhold avelumab therapy Increase frequency of monitoring to every 3 days 1.0 to 2.0 mg/kg/day prednisone or equivalent. Add prophylactic antibiotics for opportunistic infections Consider renal biopsy
	
If returns to Baseline: Taper steroids over at least 1 month, and resume avelumab therapy following steroids taper. If worsens: Treat as Grade 4.

Grade 4 Creatinine increased > 6 x ULN
	
Permanently discontinue avelumab therapy Monitor creatinine daily 1.0 to 2.0 mg/kg/day prednisone or equivalent. Add prophylactic antibiotics for opportunistic infections Consider renal biopsy Nephrology consult
	
If returns to Baseline: Taper steroids over at least 1 month.

Cardiac irAES		

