
Grade 3 or Grade 4 endocrinopathies (hypothyroidism, hyperthyroidism, adrenal insufficiency, type I diabetes mellitus)
	
Withhold avelumab therapy Consider hospitalization Endocrinology consult
 
Start thyroid hormone replacement therapy (for hypothyroidism), anti-thyroid treatment (for hyperthyroidism), corticosteroids (for adrenal insufficiency), or insulin (for type I diabetes mellitus) as appropriate.
 
Rule-out secondary endocrinopathies (ie, hypopituitarism / hypophysitis)
	
Resume avelumab once symptoms and/or laboratory tests improve (with or without hormone replacement/suppression).
 
Continue hormone replacement/suppression and monitoring of endocrine function as appropriate

Hypopituitarism/Hypophysitis (secondary endocrinopathies)
	
If secondary thyroid and/or adrenal insufficiency is confirmed (ie, subnormal serum T4 with inappropriately low TSH and/or low serum cortisol with inappropriately low ACTH) :
 
 
Refer to endocrinologist for dynamic testing as indicated and measurement of other hormones (FSH, LH, GH/IGF-1, prolactin, testosterone in men, estrogens in women)
 
Start hormone replacement/suppressive therapy as appropriate
 
Perform pituitary MRI and visual field examination as indicated
 
 
If hypophysitis confirmed:
 
 
Continue avelumab if mild or moderate symptoms with normal MRI. Repeat the MRI in 1 month
 
	
Resume avelumab once symptoms and hormone tests improve (with or without hormone replacement).
 
In addition, for hypophysitis with abnormal MRI, resume avelumab only once shrinkage of the pituitary gland on MRI scan is documented.
 
Continue hormone replacement/suppression therapy as appropriate.

	
 
Withhold avelumab if severe symptoms or life-threatening symptoms of hypophysitis and/or abnormal MRI. Consider hospitalization. Initiate high-dose corticosteroids (1 to 2 mg/kg/day methylprednisolone iv or equivalent) followed by corticosteroids taper during at least 1 month.
 
	
Other irAEs (not described above)		
Grade of other irAEs (NCI-CTCAE v4.03)	Grade of other irAEs (NCI-CTCAE v4.03)	Grade of other irAEs (NCI-CTCAE v4.03)

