Grade 2 or Grade 3 clinical signs or symptoms suggestive of a potential irAE	Withhold avelumab therapy pending clinical investigation	If irAE is ruled out, manage as appropriate according to the diagnosis and consider re-starting avelumab therapy If irAE is confirmed, treat as Grade 2 or 3 irAE
Grade 2 irAE or first occurrence of Grade 3 irAE	Withhold avelumab therapy 1.0 to 2.0 mg/kg/day prednisone or equivalent Add prophylactic antibiotics for opportunistic infections Specialty consult as appropriate	If improves to Grade 1: Taper steroids over at least 1 month and resume avelumab therapy following steroids taper
Recurrence of same Grade 3 irAEs	Permanently discontinue avelumab therapy 1.0 to 2.0 mg/kg/day prednisone or equivalent Add prophylactic antibiotics for opportunistic infections Specialty consult as appropriate	If improves to Grade 1: Taper steroids over at least 1 month
Grade 4	Permanently discontinue avelumab therapy 1.0 to 2.0 mg/kg/day prednisone or equivalent and/or other immunosuppressant as needed Add prophylactic antibiotics for opportunistic infections Specialty consult.	If improves to Grade 1: Taper steroids over at least 1 month

Requirement for 10 mg per day or greater prednisone or equivalent for more than 12 weeks for reasons other than hormonal replacement for adrenal insufficiency	Permanently discontinue avelumab therapy Specialty consult	
Persistent Grade 2 or 3 irAE lasting 12 weeks or longer		

ACTH: adrenocorticotropic hormone; ADL: activities of daily living; ALT: alanine aminotransferase; AST: aspartate aminotransferase; BNP: B-type natriuretic peptide; CK-MB: creatine kinase-myocardial fraction b; CT: computed tomography; FSH: follicle stimulating hormone; GH: growth hormone; IGF-1: insulin-like growth factor; irAE: immune-related adverse event; LH: luteinizing hormone; MRI: magnetic resonance imaging; NCI-CTCAE: National Cancer Institute Common Terminology Criteria for Adverse Event; T4: free thyroxine; TSH: thyroid-stimulating hormone; ULN: upper limit of normal.

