8.1 Definition of Protocol Deviations and Analysis Sets

Important protocol deviations (IPDs) are protocol deviations that might significantly affect the completeness, accuracy, and/or reliability of the study data or that might significantly affect a subject's rights, safety, or well-being.

IPDs include:

- Subjects that are dosed on the study despite not satisfying the inclusion criteria;
- Subjects that develop withdrawal criteria whilst on the study but are not withdrawn;
- Subjects that receive the wrong treatment or a significantly incorrect dose;
- Subjects that receive an excluded concomitant medication;
- Deviation from Good Clinical Practice (GCP).

The following deviations will be identified and confirmed prior to or at the Data Review Meeting at the latest.

- IPDs as defined above
- Deviations from the inclusion and exclusion criteria
- Deviations post inclusion

All IPDs will be documented in the study data tabulation model (SDTM) datasets whether identified through site monitoring, medical review or programming.

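### Protocol 5.1.3.2 requires permanent discontinuation after Grade 3 and 4 reactions for which Table 5 resumes avelumab, and no text says which prevails

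*Protocol*

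**What the plan says.** **Protocol 5.1.3.2** introduces its list with "The following adverse drug reactions (ADRs; for definition, see Section 7.4.1.1) require permanent treatment discontinuation of avelumab". The list covers any Grade 4 ADR with four exceptions and any Grade 3 ADR with six. For Grade 2 it says "Infusion should not be given in case of ongoing Grade 2 ADR on the day of trial treatment administration". It closes by pointing the reader to the irAE guidance in 6.5.5.3.

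**Protocol 5.5.1** lists reasons for mandatory withdrawal from avelumab. One is the occurrence of any Grade 3 or higher "ADRs or as defined in Section 5.1.3.2". Section 6.2.1 makes 5.5.1 operative, because dosing runs until its criteria are met.

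**Protocol 6.5.5.3** says irAE treatment should follow Table 5. In Table 5:

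- Grade 3 or 4 endocrinopathy: withhold, then "Resume avelumab once symptoms and/or laboratory tests improve (with or without hormone replacement/suppression".
- Grade 2 to 3 creatinine increase: withhold, then on return to baseline "Taper steroids over at least 1 month, and resume avelumab therapy following steroids taper".
- The row headed "Grade 2 irAE or first occurrence of Grade 3 irAE" (other irAEs): withhold, then resume after a steroid taper.
- Initial Grade 3 diarrhea or colitis and initial Grade 3 rash: withhold, then resume after a taper.
- Grade 1 to 2 rash: "Continue avelumab therapy Symptomatic therapy (eg, antihistamines, topical steroids".

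**SAP 8.1** counts as an important protocol deviation: "Subjects that develop withdrawal criteria whilst on the study but are not withdrawn". SAP 10.2.1 repeats the item. Neither says which protocol section defines the withdrawal criteria.

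**The concern.** Protocol 7.4.1.1 defines an ADR as any adverse event that the investigator or sponsor suspects is related to treatment. A treatment-related irAE is therefore an ADR, and both 5.1.3.2 and Table 5 govern it. Where they differ, one text ends treatment for good and the other restarts it. Two sites, each following the protocol, could then handle the same child's reaction in opposite ways.

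That bears first on the safety of children who have had a severe reaction. It also makes exposure and the count of discontinuations due to adverse events depend partly on which section a site read. Lastly, it leaves unsettled whether a child re-treated under Table 5 has a protocol deviation at all.

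**Working it through.** No figure in the plan is at issue, so the check is a comparison by reaction and grade. For each Table 5 row that resumes or continues avelumab, I asked whether an exception in 5.1.3.2 covers it.

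| Reaction | 5.1.3.2 | Table 5 | Result |
|---|---|---|---|
| Grade 3 or 4 endocrinopathy | No endocrine exception at either grade: stop | Withhold, then resume | Conflict |
| Initial Grade 3 colitis | Exception names diarrhea and skin toxicity, not colitis: stop | Withhold, then resume after taper | Conflict |
| Initial Grade 3 diarrhea or rash | Excepted only if Grade 1 or lower in under 7 days from start of management | Withhold, then resume after taper, with no limit on time to improvement | Conflict when resolution takes 7 days or more |
| First Grade 3 irAE of another type | No such exception: stop | Withhold, then resume after taper | Conflict |
| Grade 3 creatinine | Excepted if a single laboratory value without clinical correlate | Withhold, then resume after taper | Conflict only with a clinical correlate |
| Grade 2 rash | No infusion while ongoing | Continue; withhold if it persists beyond 1 to 2 weeks or recurs | Hold versus continue on a dosing day |

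Three further points.

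1. **The diarrhea and rash conflict is not hypothetical.** For Grade 3 to 4 diarrhea that worsens, persists beyond 3 to 5 days or recurs, Table 5 adds infliximab. For an initial Grade 3 event it sets no point at which slow resolution rules out resuming.
2. **Not every row conflicts.** Grade 3 to 4 pneumonitis, Grade 4 diarrhea, colitis and rash, recurrence of the same Grade 3 irAE in the other-irAE rows, and Grade 4 irAEs of other types end in permanent discontinuation in Table 5, as 5.1.3.2 also requires.
3. **The SAP step is conditional.** Take a child with a first Grade 3 irAE of another type who improves to Grade 1, completes the taper and is dosed again. If the withdrawal criteria are those of 5.5.1 and 5.1.3.2, the child met them and was not withdrawn, which is an important deviation under SAP 8.1 and 10.2.1. If Table 5 prevails for irAEs, there is no deviation. The facts are the same and the classification is opposite.

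**The case against.** The best defense is that 5.1.3.2 is the general rule for ADRs and Table 5 the specific rule for irAEs. Several places support it: 5.1.3.2 ends by pointing to 6.5.5.3; 6.5.5.3 says to follow Table 5; 5.2 says suspected immune-mediated events are managed by the protocol's guidelines; and 6.5.4 sends irAE management to 6.5.5.3. This makes the Table 5 reading reasonable but does not settle the matter. None of these places limits the mandatory list in 5.1.3.2. That list also appears to have immune-mediated reactions in view, since its diarrhea and skin exception gives immunosuppressant treatment as an example of management and still sets a 7-day limit.

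Four stronger readings are tempting, and the documents do not support them:

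- **That 5.5.1 is a third, unconditional stopping rule.** Its line can be read as a pointer to 5.1.3.2 with the exceptions included; an unconditional Grade 3 trigger would make those exceptions pointless. The wording is unclear, and no more than that can be said.
- **That Grade 3 creatinine conflicts outright.** The renal row is graded on creatinine alone, so the single-laboratory-value exception may apply. A purely laboratory Grade 3 endocrine finding might be argued the same way; a symptomatic one could not.
- **That Grade 2 reactions have incompatible stopping rules.** For rash, neither text requires withdrawal, and an ongoing Grade 2 ADR is not in itself a withdrawal criterion in 5.5.1.
- **That every Table 5 re-treatment is a deviation that damages the analysis.** The SAP lists important deviations, confirms them by the Data Review Meeting, places their management outside the plan, and defines no per-protocol set. Exclusion from the PK Analysis Set would arise only if the deviation were judged to affect PK, on the natural reading of SAP 8.2. The discontinuation tables report the recorded action and stay accurate as records.

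**Conclusion.** The contradiction is real between 5.1.3.2 and Table 5. It covers four situations without a stated resolution: Grade 3 or 4 endocrinopathy, initial Grade 3 colitis, initial Grade 3 diarrhea or rash not resolved within the 7-day limit, and a first Grade 3 irAE of another type. Grade 3 creatinine is a conditional fifth. Grade 2 rash is a lesser inconsistency about whether to dose on the day.

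The number of children affected cannot be estimated. Phase I plans 12 to 36 subjects, the documents give no rate for these events, and protocol 5.2 says most irAEs have been mild.

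A reader might infer that the primary analysis of Grade 3 or higher treatment-emergent events is compromised. The documents do not show that. The triggering reaction is counted whether or not avelumab is later resumed; what resumption changes is the length of the on-treatment period, which ends 30 days after the last dose or the day before new anticancer drug therapy, whichever is earlier. A Grade 2 hold on Day 15 might be argued to bear on the dose-limiting toxicity criterion of completing two infusions. Whether it counts would be a matter for the Safety Monitoring Committee's assessment, on which the SAP bases that analysis.

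The conclusion assumes that the reaction is judged related to avelumab. The deviation consequence also assumes that 5.5.1 and 5.1.3.2 are taken as the withdrawal criteria.

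**What to change.** 1. Reconcile 5.1.3.2, 5.5.1 and Table 5 so that each reaction and grade has one instruction, and state which text prevails for irAEs. Which clinical rule applies is for the clinical team.
2. Make the ADR line in 5.5.1 refer only to the reconciled rule, so that it is clear whether the exceptions apply.
3. In SAP 8.1 and 10.2.1, cite that rule as the definition of withdrawal criteria for the deviation item.

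The cost is a protocol amendment or clarification and a sentence in the SAP, with no added subjects, visits or procedures. SAP version 2.0 records that pediatric monotherapy evaluation ended after Phase I, so the protocol change now helps only subjects still on treatment and any reuse of this text. The SAP sentence remains useful: the important-deviation list is to be final before database lock, and the rule used to classify re-treated children should be on record by then.

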## 5.2 Discussion of Trial Design

In the Phase I dose-finding part of the study, the RP2D in children 0 to < 18 years of age will be determined. In Phase II, 2 expansion cohorts will be opened in 2 specified tumor types selected based on emerging data from this and other ongoing studies. These data may include clinical data with avelumab or with other ICIs, or preclinical data providing additional rationale in a specific tumor type.

Subjects will not be selected for enrollment in either Phase I or Phase II part of the study based on any molecular characteristics, such as PD-L1 expression, because the optimal strategy for selection of pediatric subjects who derive maximum benefit from avelumab is currently unknown.

Because the benefit of avelumab in pediatric subjects with cancer has not yet been established, eligibility criteria are aimed to ensure that the subjects have exhausted available standard therapy. In addition, a standard set of criteria for avelumab studies has been incorporated, such as exclusion of subjects previously treated with an ICI, absence of active autoimmune disease that can be exacerbated by avelumab, and adequate organ function.

### Justification for Dose

The Phase I, dose-finding part of the study will establish the RP2D of avelumab in pediatric subjects. The starting dose will be the same as the recommended adult dosing regimen, 10 mg/kg every 2 weeks. Treatment will continue until confirmed progression, death, unacceptable toxicity, or any criterion for withdrawal occurs. The adult dose was selected as the starting dose in this study for several reasons, as described below.

In a clinical trial of adult cancer subjects treated with avelumab at doses ranging from 1 mg/kg to 20 mg/kg (Study EMR100070-001), the MTD was not reached. A dose of 10 mg/kg every 2 weeks was chosen as the dose regimen expected to achieve > 95% target occupancy in all subjects (refer to Section 5.2 of the IB).

Simulation was conducted based on the adult PopPK model to find a dose that would have exposure similar to that observed in adult population. First-cycle PK data showed that the

exposures were similar or tended to be lower in subjects with lower body weights following administration of avelumab 10 mg/kg iv every 2 weeks. In the first simulation, the clearance (CL) was assumed to be related to body weight as a power function, with exponents of 0.85 on CL and of 1 on volume of distribution (V) as reported in the literature (Deng 2011). An alternative model using estimated exponent (0.565 for CL and 0.472 for central volume) from the adult Pop PK model had been also explored. It had been noted that allometric exponents estimated from data within species (such as adult subjects) were typically smaller than those observed for between-species scaling, which was likely due to a narrower body weight range in adults for a given species (approximately 2- to 3-fold) (Bai 2012). For this reasons, the first simulation with fixed exponents for CL (0.85) and V (1) was considered to be more relevant for a population like children with a wide range of body weights. This model predicted that 10 mg/kg was needed to achieve similar or relatively lower exposure in children to that in adults, and 15 to 20 mg/kg dose would potentially lead to a higher exposure in children than that in the adults. Therefore, 10 mg/kg was recommended for the starting dose to avoid potential overexposure in some of the body weight groups.

Ongoing pediatric studies with other PD-L1 antibodies (nivolumab, pembrolizumab, atezolizumab) were initiated at the adult approved dose (Bristol Myers Squibb 2013; Merck, Sharp & Dohme 2015; Georger 2017b). This is also consistent with recent experience with other targeted agents in pediatric oncology. A recent study examined dose-finding studies of 15 predominately small molecular targeted agents (Paoletti 2013). For 75% of the compounds, the pediatric RP2D was between 90% and 130% of the adult dose, and the findings were similar to those reported in adults in terms of either MTD/MAD or RP2D, and PK conclusions. The traditional approach of starting below the adult dose resulted in more than 60% of children being underdosed. Of note, 3 monoclonal antibodies were among the 15 molecular targeted agents. For all 3, the pediatric RP2D was the same as in adults (Paoletti 2013). Taken together, these data suggest that for biologics in general, and for ICIs in particular, selection of the adult dose as the starting dose in children is appropriate.

Similarly, there is no evidence to indicate that the avelumab safety profile should be different in children compared with adults. In the pediatric studies of ipilimumab, pembrolizumab, atezolizumab, and nivolumab, the nature and timing of irAEs was similar to that seen in adults (Merchant 2016). Therefore, there are limited data to suggest that children are at increased risk of irAEs (Davis 2017; Georger, 2017a; Georger, 2017b). The safety of avelumab in pediatric subjects will be characterized using standard methods (eg, characterization of AEs, laboratory abnormalities, vital signs).

Avelumab is characterized by 2 main recognized types of adverse events: irAEs and IRRs (refer to IB, Section 5.3.1.3.1.6 and Section 5.3.1.3.1.7). Because inhibition of PD-L1 stimulates the immune system, inflammatory reactions collectively referred to as irAEs might occur (Weber 2015; Postow 2015; Naidoo 2015). Immune-related AEs are a known class effect of ICIs and may include pneumonitis, colitis, hepatitis, endocrinopathies, dermatitis, nephritis and renal dysfunction, encephalitis, eye disorders (including uveitis and iritis), and other immune-mediated reactions (including myositis and myocarditis). The majority of irAEs have been mild and respond to immunosuppressive treatment (ie, glucocorticoids). Guidance is provided to Investigators that any AE suspected to have an underlying immune-mediated mechanism, and without other confirmed etiology, should be considered immune related and managed according to guidelines described in the protocol.

In addition to irAEs, the other recognized toxicity of avelumab is IRRs (refer to the IB for additional information). Infusion-related reactions frequently occur with other monoclonal antibodies commonly used in children, including rituximab and infliximab. Studies suggest that the rate of infusion reactions is similar in adults and in children, including children  $\leq 5$  years old (Dale 2014; Aeschlimann 2014).

Little is known about the long-term effects of checkpoint inhibition on the developing immune system, although preclinical data suggest a role for PD-L1 in the development and function of T cells (Francisco 2009). Reassuringly, there were no changes in absolute lymphocyte count and in frequency of immune-cell subsets in peripheral blood mononuclear cells obtained from adult cancer subjects pre- and post-treatment with avelumab (Lepone 2015). Given the expected poor survival of the subject population to be enrolled on this trial, the potential benefit of therapeutic effect outweighs the theoretical risk of long-term immune dysfunction.

In summary, based on the wide therapeutic index and the lack of specific safety concerns in the pediatric age group, the starting dose in the dose-finding part of the study was selected to be the adult RP2D, 10 mg/kg every 2 weeks. Detailed guidelines on the early recognition and management of irAEs and IRRs will be provided to the Investigators, subjects, and caregivers.

